4. OBJECTIVE(S)/SPECIFIC AIMS AND HYPOTHESES

- *A concise statement of the goal(s) of the current study.*
- *The rationale for and specific objectives of the study.*
- *The goals and the hypothesis to be tested should be stated.*

The aim of the study is to compare the efficacy of dexamethasone at the current recommended dose versus a higher, weight-based dose. We hypothesize that the use of a higher, weight-based dose of dexamethasone equivalent to 1 mg/kg/day of methylprednisolone would be associated with a decrease in mortality in COVID-19 patients requiring oxygen supplementation.

Primary outcome:

- All-cause mortality at 28 days

Secondary outcomes:

- ICU admission
- ICU length of stay
- Hospital length of stay
- Need for higher oxygen supplementation including venturi mask, non-rebreather mask, high flow nasal cannula or non-invasive mechanical ventilation
- Invasive mechanical ventilation
- Duration of invasive mechanical ventilation
- ECMO
- Need for tracheostomy
- Development of secondary bacterial or fungal infections
- Development of clinically significant hyperglycemia, which will be defined as need for insulin drip or ICU admission to control hyperglycemia
- Oxygen supplementation upon discharge from the hospital
- Subjective symptoms at 28 days
- Disposition upon discharge (home, home with physical therapy, skilled nursing facility, long-term acute care facility, long-term care facility / nursing home, acute rehabilitation facility, hospice care, death)

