10. ENDPOINTS

- *Describe the primary and secondary study endpoints*
- *Describe any primary or secondary safety endpoints*

Primary study endpoint: all-cause mortality at 28 days.

Secondary study endpoints: need for ICU admission, ICU length of stay, hospital length of stay, higher requirements of oxygen supplementation (venturi mask, non-rebreather mask, high-flow nasal cannula or non-invasive mechanical ventilation), invasive mechanical ventilation, duration of invasive mechanical ventilation, ECMO, tracheostomy, subjective symptoms at 28 days, disposition upon discharge, and oxygen supplementation upon discharge.

The primary and secondary safety endpoints will include the development of secondary bacterial or fungal infections that is objectively identified based on culture data, and clinically significant hyperglycemia requiring ICU stay or insulin drip.

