Data to be collected will include baseline demographic variables, need for higher requirements of oxygen supplementation (venturi mask, non-rebreather mask, high flow nasal cannula or non-invasive mechanical ventilation), ICU admission, invasive mechanical ventilation, duration of invasive mechanical ventilation, tracheostomy, ECMO, length of ICU stay, length of hospital stay, development of secondary bacterial or fungal infections, subjective symptoms at 28 days, development of clinically significant hyperglycemia, oxygen supplementation upon discharge and disposition upon discharge (home, home with physical therapy, skilled nursing facility, long-term acute care facility, long-term care facility / nursing home, acute rehabilitation facility, hospice care, death)

An interim safety and result analysis will be performed after the first 20 patients are enrolled in the study. Subsequent monitoring will occur when 50 and 100 patients are recruited. A designated committee from the study will be assigned for this purpose.]

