12. STATISTICAL ANALYSIS

- *Describe how your data will be used to test the hypotheses.*
- *State clearly what variables will be tested and what statistical tests will be used.*
- *Include sample size calculations.*

- *If this is a pilot study, state which variables will be examined for hypothesis generation in later studies.*

In general, baseline patient characteristics including demographics and clinical data will be summarized using descriptive statistics for all data combined and data by treatment arm. Specifically, continuous variables will be summarized using mean, standard deviation and median; categorical variables will be summarized using frequencies and percentage. No inferential comparison of treatment arms will be made with respect to baseline and demographic clinical data; such comparisons will be descriptive only. Unless otherwise specified, all results will be considered significant if $p < 0.05$. All data analysis will be performed using SAS 9.4 (SAS institute Inc., Cary, NC). The intent-to-treat (ITT) principle will be employed, i.e all randomized patients in the groups to which they are randomly assigned will be included in the final analysis, regardless of the intervention they actually receive, and regardless of withdrawal from treatment or deviation from the protocol for any reason.

The primary endpoint is all-cause mortality at 28 days. It will be compared between the two treatment arms using chi-squared test or Fisher's exact test.

Among the secondary study endpoints, binary variables (need for ICU admission, need for higher oxygen supplementation including non-rebreather mask, high flow nasal cannula or non-invasive mechanical ventilation, need for invasive mechanical ventilation and need for oxygen supplementation upon discharge) will be compared using chi-squared test or Fisher's exact test between the two arms; continuous variables (ICU length of stay, hospital length of stay, duration of mechanical ventilation) will be compared between the two arms using Kaplan-Meier curve and log-ran test to take into account data censoring.

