Sample size consideration: The sample size calculation was based on the hypothesis of primary endpoint. Our primary hypothesis is that the use of a higher dose of dexamethasone equivalent to 1 mg/kg/day of methylprednisolone would be associated with a decrease in mortality in COVID-19 patients requiring oxygen supplementation. A two group χ^2 test with a 5% two-sided significance level will have 80% power to detect the difference between the proportion of dexamethasone 6 mg group 23.3% and the proportion of dexamethasone weight based 5.9% (odds ratio of 0.206) when the sample size in each group is 64.

To account for 10% dropout rate, will be increasing recruitment to 142, with 71 in each arm to ensure 128 evaluable subjects.

Missing data: If there is less than 5% of an endpoint missing, complete case analysis will be used; if there is more than 5% missing, sensitivity analysis will be performed by assuming all the missing values of an endpoint to be either outcome if it is binary, or by assuming all the missing values of an endpoint to be either upper quartile or lower quartile of the available values if it is continuous, to see if the results are similar to those using complete case analysis.

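### The Kaplan-Meier and log-rank plan for hospital stay, ICU stay and ventilation duration has no rule for death, nor for patients with no ICU stay or ventilation, while planned mortality is 23.3% v 5.9%

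*Combined protocol and SAP*

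**What the plan says.** Section 12 (Statistical Analysis) gives the method for the three duration endpoints: "continuous variables (ICU length of stay, hospital length of stay, duration of mechanical ventilation) will be compared between the two arms using Kaplan-Meier curve" and a log-rank "test to take into account data censoring". It does not say what is censored, or when.

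Other text that bears on the point:

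- **Population.** Section 12 applies intention to treat: "all randomized patients in the groups to which they are randomly assigned will be included in the final analysis".
- **Endpoint names.** Section 10 (Endpoints) lists "need for ICU admission, ICU length of stay, hospital length of stay, higher requirements of oxygen supplementation" and others without defining an event or a time origin. Section 11 (Research Procedures) lists "length of ICU stay, length of hospital stay" among the data to collect.
- **Disposition.** In Section 4 (Objectives) the categories of disposition upon discharge end with "acute rehabilitation facility, hospice care, death". Section 11 repeats them.
- **Missing data.** For continuous endpoints Section 12 plans a sensitivity analysis "assuming all the missing values of an endpoint to be either upper quartile or lower quartile of the available values if it is continuous". Death is not mentioned there.
- **Planned mortality.** The sample size in Section 12 rests on the "proportion of dexamethasone 6 mg group 23.3% and the proportion of dexamethasone weight based 5.9" (per cent).
- **Follow-up.** Section 9 (Study Timelines) ends participation at 28 days or at discharge, whichever is first. Section 20 (privacy provisions) adds a survey or telephone call to establish the primary endpoint in patients discharged before day 28.

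**The concern.** A log-rank test compares times to an event, so its meaning depends on what the event is and what is censored. For a hospital stay that can end in discharge alive or in death, the plan leaves open at least two ordinary rules.

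- **Death ends the stay.** An early death scores as a short stay. This is a legitimate measure of bed use, but a shorter stay cannot then be read as benefit.
- **Death is censored at its date.** Log-rank then tests the cause-specific hazard of discharge alive, which is a valid target. One minus Kaplan-Meier, however, no longer estimates the share discharged alive. It overstates that share, and by more in the arm with more deaths.

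The text points both ways. Listing death as a discharge disposition suggests the first rule, and the reference to censoring could be read as the second. If the primary hypothesis is right, death removes patients about four times as often in the 6 mg arm, so the rule matters most when the trial succeeds. Left unstated, it can be chosen after the data are seen.

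For ICU stay and ventilation there is a second gap. Intention to treat keeps all randomized patients, but no value is given for those who were never admitted or never ventilated.

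**Working it through.** **1. The plan's own figure.** Inputs from Section 12: 23.3% v 5.9%, two-sided 5%, 80% power. The mean proportion is (0.233 + 0.059)/2 = 0.146.

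n = [1.96 × √(2 × 0.146 × 0.854) + 0.8416 × √(0.233 × 0.767 + 0.059 × 0.941)]² / (0.233 − 0.059)² = (0.979 + 0.407)² / 0.0303 = 63.5, so 64 per arm. The stated 64 is reproduced.

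**2. Deaths implied by the same rates.** 71 × 0.233 = 16.5 and 71 × 0.059 = 4.2, a ratio of 3.95. At 64 per arm, 14.9 v 3.8. These are all deaths to day 28; in-hospital deaths are fewer if some follow discharge.

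**3. The curve when death is censored.** Assume constant hazards and the same discharge hazard in both arms, with median 10 days: λ = ln 2/10 = 0.0693 per day. Death hazards μ of 0.0233 and 0.0050 per day give 23.3% and 5.9% mortality by day 28.

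- One minus Kaplan-Meier estimates 1 − exp(−28λ) = 1 − exp(−1.941) = 86% in both arms.
- The true share discharged alive is λ/(λ+μ) × [1 − exp(−28(λ+μ))].
- 6 mg arm: 0.748 × 0.925 = 69%.
- Weight-based arm: 0.933 × 0.875 = 82%.

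The curve overstates live discharge by 17 and 4 points and hides a 13-point difference. The log-rank test itself rejects in 5.2% of trials, as it should, because the discharge hazards are equal.

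**4. The test under different death rules.** The documents give no stay or death times, so these are assumed: survivor stay lognormal with median 8 days (log-SD 0.6), identical in both arms; median day of death 5, 10 or 14 (log-SD 0.5), with death times kept within 28 days; all deaths in hospital; 71 per arm; 10,000 trials per scenario. Entries are shares of trials with two-sided p < 0.05. Longer and shorter refer to the weight-based arm.

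| Rule | Day 5 | Day 10 | Day 14 |
|---|---|---|---|
| Death ends stay: longer | 10.8% | 1.5% | 0.4% |
| Death ends stay: shorter | 0.4% | 4.2% | 11.6% |
| Death censored: shorter | 7.1% | 25.8% | 40.8% |
| The two rules disagree on significance | 17% | 23% | 30% |

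Repeat runs put the disagreement at about 16–30%. Holding deaths to day 28 as not discharged, which approximates Gray's test here, gives shorter in 69–70%. Counting any pair of the three rules, a significant reversal of direction occurs in 4.9%, 0.2% and 0.0% of trials.

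**5. Checks.**

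- Equal mortality of 14.6% in both arms: each rule rejects in 5–6%, so the effect comes from unequal deaths.
- 23.3% v 15%: the two log-rank rules disagree in about 8–10%, and censoring gives shorter in 4–13%.
- 80% of deaths in hospital: censoring gives shorter in 6–29%.

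**The case against.** The strongest reply is that the plan can be read as complete. Death is a listed discharge disposition, so death ends the stay. Censoring then means patients still in hospital at day 28 or withdrawn, and intention to treat fixes the population. On that reading the main scenarios reject in 11.2%, 5.7% and 12.0% of trials (both directions summed), only modestly above 5%. This reading is natural, but it is an inference: Section 12 does not state it, and the result would be a bed-use measure that the plan does not label as one.

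Four stronger readings are tempting, and the documents do not support them.

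- A reader might infer that no population is set. The intention-to-treat sentence sets it; only the value for never-admitted and never-ventilated patients is missing.
- A reader might infer that the rule usually decides significance. The two log-rank rules disagree in a minority of trials. The share passes one half only when the Gray-type rule, which the plan does not name, is added, and only near the full planned effect.
- A reader might infer that the direction of effect is at risk. Significant reversals are rare.
- A reader might infer that log-rank with death censored is invalid unless death and discharge are independent. It tests the cause-specific hazard regardless. Independence is needed only to read the result as what would happen without deaths.

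It also stands that Gray's test is not neutral evidence. In these runs it favours the weight-based arm in 78% of trials with a significant primary result and in 12–14% of the others, and its correlation with the primary z is 0.78.

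**Conclusion.** The concern holds for the death rule and for the missing zero-day statement. The plan names a method whose result and interpretation depend on how death is treated, and it does not say how, while planning for about 16.5 v 4.2 deaths per 71. The curve distortion (86% in both arms against 69% and 82%) rests on constant hazards and a 10-day median time to discharge. The 16–30% disagreement rests on assumed stay and death times, deaths in hospital and the full planned effect; at 23.3% v 15% it falls to about 8–10%. These figures show the size of the ambiguity and do not predict results. The primary mortality comparison and the sample size are unaffected.

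**What to change.** In Section 12:

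1. **Hospital stay.** Define the event as discharge alive by day 28, with death as a competing event. State whether discharge to hospice counts as discharge alive.
2. **Method.** Replace Kaplan-Meier with cumulative incidence curves and Gray's test as the main analysis, with the cause-specific log-rank as supportive. Report deaths and survivors' stay beside it, because Gray's test partly re-expresses the mortality difference.
3. **If bed use is the aim.** Keep death as the end of stay, and label the result as resource use and not as benefit.
4. **ICU stay and ventilation.** Apply the same death rule, keep all randomized patients, and state that those never admitted or never ventilated count as zero days.

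The cost is SAP wording: lengths of stay and disposition, including death and hospice, are already collected (Section 11). The rule should be fixed before outcome data are seen.

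An optional alternative for ICU stay and ventilation is ICU-free and ventilator-free days to day 28, with death scored 0. It costs more. The endpoint lists in Sections 2, 4 and 10 would change. Because participation can end at discharge, it also needs a stated no-readmission assumption or one question added to the existing day-28 contact. The score mixes death with duration, so its components would have to be shown.

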9. STUDY TIMELINES

- *Describe the duration of an individual's participation in the study*
- *Describe the duration anticipated to enroll all study subjects*
- *The estimated date of study completion*

The duration of an individual's participation in the study will be 28 days or until hospital discharge, whichever occurs first.

The duration anticipated to enroll all study subjects is 6 months.

The estimated date of study completion is 12 months.

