16. WITHDRAWAL OF SUBJECTS

- *Describe anticipated circumstances under which subjects will be withdrawn from the research without their consent*
- *Describe procedures for orderly termination*
- *Describe procedures that will be followed when subjects withdraw from the research, including partial withdrawal from procedures with continued data collection.*

Patients may choose to withdraw from the study at any time. They will be asked to provide a reason for withdrawal if they choose to and will be asked if investigators can follow the electronic health record data over time until the study is completed.

Participants may be withdrawn from the study if deemed appropriate by clinician judgement. Data will be analyzed as intention-to-treat.

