20. PROVISIONS TO PROTECT PRIVACY INTERESTS OF SUBJECTS

- *Describe the methods used to identify potential research subjects, obtain consent and gather information about subjects to ensure that their privacy is not invaded.*
- *In addition consider privacy protections that may be needed due to communications with subjects (such as phone messages or mail).*

Potential research subjects will be screened via Sunrise. Investigators will review the oxygen saturation and oxygen requirements of patients admitted to the COVID floors and review for eligibility. For patients who are discharged prior to 28 days, a survey will be sent out via email using REDCap to determine primary endpoint and subjective symptoms. Only relevant information will be collected and stored directly into REDCap. For patients without access to email or who do not respond to the survey, a follow up phone call will be made. Only information relevant to the research will be reviewed to ensure patient privacy.

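### Day-28 mortality: the missing-data rule requires no check below 5% missing and only a same-outcome-for-everyone check above it, so it can miss dependence on arm-specific unobserved deaths

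*Combined protocol and SAP*

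**What the plan says.** Section 12 (Statistical Analysis) gives the missing-data rule in two branches.

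- Below the threshold: "If there is less than 5% of an endpoint missing, complete case analysis will be used". No sensitivity analysis is attached.
- Above it, a binary endpoint is re-analysed "by assuming all the missing values of an endpoint to be either outcome if it is binary", and the result is compared with the complete-case result. Treatment arm is not mentioned. The natural reading is that every missing patient, in either arm, receives the same outcome.

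No other section adds a sensitivity analysis for day-28 mortality.

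Four other statements bear on the point:

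- Section 12 applies intention to treat: "all randomized patients in the groups to which they are randomly assigned will be included in the final analysis". It covers withdrawal from treatment and protocol deviations, but not unobserved outcomes.
- The sample size is raised from 128 to 142: "To account for 10% dropout rate". The plan therefore budgets for the branch above 5%.
- For patients discharged before day 28, Section 20 says "a survey will be sent out via email using REDCap to determine primary endpoint and subjective symptoms", and then "For patients without access to email or who do not respond to the survey, a follow up phone call will be made". Under Section 16, patients who withdraw "will be asked if investigators can follow the electronic health record data over time until the study is completed".
- Section 9 sets participation at "28 days or until hospital discharge, whichever occurs first".

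**The concern.** In-hospital deaths will be in the electronic record, so unknown day-28 status should arise mainly after discharge or withdrawal. After discharge it depends on a reply to a survey or a phone call. A patient who has died cannot reply, so non-response may be related to the outcome itself, which is the setting where complete-case analysis is weakest. Section 9, which ends participation at discharge, must be reconciled with the survey in Section 20; as written, it could itself produce missing outcomes.

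Few events are expected, about 19 deaths among 128 evaluable patients, so a handful of unobserved deaths can move the primary result across 0.05. The uniform check responds when missing counts differ between arms. With similar counts it adds about the same number of deaths to both arms and leaves the difference largely intact. A result could then be reported as robust without the reader learning that two or three unobserved deaths in one arm would overturn it.

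**Working it through.** **Inputs (Section 12):** mortality 23.3% versus 5.9%; two-sided 5% chi-squared test with 80% power; 64 evaluable and 71 recruited per arm; chi-squared or Fisher's exact test for the primary comparison.

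**The plan's own figure.** The mean rate is (0.233 + 0.059)/2 = 0.146. Then n = [1.960 √(2 × 0.146 × 0.854) + 0.842 √(0.233 × 0.767 + 0.059 × 0.941)]² / 0.174² = 63.5, which rounds up to 64 per arm, as stated.

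**Threshold and events.** 7/142 = 4.93% and 8/142 = 5.63%, so the first branch covers up to 7 missing patients. Expected deaths are 64 × 0.233 + 64 × 0.059 = 18.7.

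**Above 5%.** Assume the 10% allowance is entirely missing outcomes, 7 per arm, with 15/64 and 4/64 observed deaths (near the planning rates). Tests are Pearson chi-squared without continuity correction and two-sided Fisher.

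| Analysis | Standard | High dose | Chi-squared p | Fisher p |
|---|---|---|---|---|
| Complete case | 15/64 | 4/64 | 0.006 | 0.011 |
| All missing dead | 22/71 | 11/71 | 0.029 | 0.046 |
| All missing alive | 15/71 | 4/71 | 0.007 | 0.012 |
| 0 standard, 2 high-dose deaths | 15/71 | 6/71 | 0.033 | 0.057 |
| 0 standard, 3 high-dose deaths | 15/71 | 7/71 | 0.064 | 0.103 |
| 0 standard, 7 high-dose deaths (bound) | 15/71 | 11/71 | 0.385 | 0.516 |

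The three planned analyses all stay below 0.05 under either test. Over the full grid of 8 × 8 = 64 combinations, 46 stay significant by chi-squared and 40 by Fisher. By chi-squared, with 0, 1, 2, 3, 4 or 5 deaths among the missing standard-dose patients, significance is lost at 3, 4, 5, 5, 6 or 7 high-dose deaths. With 6 or 7 standard-dose deaths it is never lost.

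**Not one chosen table.** All possible results were enumerated with exact binomial probabilities at 23.3% and 5.9%, using chi-squared with the high dose favoured, 64 observed and 7 missing per arm:

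- significant on complete cases: 82.3%;
- significant on complete cases, all dead and all alive: 64.9%;
- of that 64.9%, lost at 2 versus 0 high-dose deaths: 7.1%; at 3 versus 0: 26.9%; at 7 versus 0: 85.7%.

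**Below 5%.** Assume 3 standard-dose and 4 high-dose patients missing, with 16/68 versus 4/67 deaths. Complete case gives p = 0.004 (Fisher 0.007). Of 4 × 5 = 20 combinations, only the extreme one (all 4 high-dose dead, all 3 standard alive: 16/71 versus 8/71) loses significance by chi-squared, p = 0.073. By Fisher, 3 of 20 do. Over all results at the planning rates, 84.9% are significant on complete cases. Of those, 22.3% are lost at 2 versus 0 high-dose deaths, and the plan would run no check.

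**Where the uniform check works.** With 5 standard-dose and 9 high-dose missing and 15/66 versus 4/62 deaths (complete case p = 0.010), all dead gives 20/71 versus 13/71, p = 0.164. With 6 and 8 missing and 15/65 versus 4/63, all dead gives 21/71 versus 12/71, p = 0.074.

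**The case against.** The planned check is not empty. At the planning rates it cuts the share of results called robust from 82% to 65%, so about a fifth of significant results are already flagged (1 − 0.649/0.823 = 21%). Near the planning rates, a 6 versus 8 split of the missing patients is enough to trigger it. This stands: the blind spot is mainly equal missingness, or more missing in the standard arm.

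The tipping cases are also unlikely without a reason for them. Three deaths among 7 against none among 7 is 43% versus 0%, the reverse of the observed direction, and the inability of a dead patient to reply applies to both arms. In the 15/64 versus 4/64 example, if missing patients in both arms die at a common 20% (an assumption), the chance of a non-significant chi-squared cell is 4.5%. At 10% it is 1.3%, and at the planning rates 0.1%. By Fisher these are 15%, 8% and 1%. This also stands: grid cells are not equally likely, and 46 of 64 is not a probability.

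Treating all dropout as unknown vital status is at the upper end, since the phone call and the record follow-up after withdrawal will recover some outcomes. Below 5% the exposure is small unless the result is near the margin.

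These points limit the weight of the concern but do not remove it. A sensitivity analysis is meant to show how strong an assumption is needed to overturn the result, and the current rule does not show that when missing counts are balanced.

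**Conclusion.** The concern holds and should be fixed. For day-28 mortality the plan requires nothing below 5% missing and only a uniform check above it, so a result can pass every planned analysis while depending on arm-specific deaths among the missing. With 7 missing per arm and deaths near the planning rates, the tipping point is 3 unobserved high-dose deaths against 0 by chi-squared, or 2 against 0 by Fisher. The gap below 5% is real but smaller. These sizes rest on assumed missing counts, their split between arms, and deaths near the planned rates; the worst case is a bound, not a forecast. The intention-to-treat statement and the complete-case rule in Section 12 also need to be reconciled for patients with unknown status.

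**What to change.** For day-28 mortality:

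1. Remove the 5% trigger and pre-specify a two-way tipping-point analysis at any level of missingness. For every combination of deaths among the missing in each arm, repeat the test used for the primary analysis. Name that test in advance, because Section 12 allows either chi-squared or Fisher and the tipping point differs between them.
2. Report missing counts by arm with reasons, the full grid, the case worst for the high-dose arm, and the boundary where p crosses 0.05. Discuss how plausible the combinations at that boundary are.
3. Keep the planned primary test on observed outcomes. Reword the intention-to-treat paragraph to say how randomized patients with unknown day-28 status are handled, and name the grid as the sensitivity analysis that retains all randomized patients. It is not a single intention-to-treat estimate.
4. Reconcile the end of participation in Section 9 with the day-28 survey in Section 20.

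The existing all-dead and all-alive checks are two corners of the grid, so nothing is lost. The cost is SAP and protocol wording and a little programming; the design, sample size and primary test do not change. The result may look less robust than under the current rule.

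### The missing-data sensitivity analysis has no arm-opposed or tipping-point scenario, so it is a weak check when loss is similar in both arms; its quartile fill also does not suit the log-rank duration endpoints

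*Combined protocol and SAP*

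**What the plan says.** All the rules are in Section 12 (Statistical Analysis).

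- **Trigger and role.** Below 5% missing for an endpoint, complete cases are analysed. Above that, "if there is more than 5% missing, sensitivity analysis will be performed", and its purpose is "to see if the results are similar to those using complete case analysis".
- **Binary endpoints.** The sensitivity analysis works by "assuming all the missing values of an endpoint to be either outcome if it is binary". No assignment by arm is mentioned.
- **Continuous endpoints.** Missing values become "either upper quartile or lower quartile of the available values if it is continuous". The text does not say whether the quartiles are pooled or taken by arm, whether a filled value counts as an event, or whether it must be at least as long as the stay already observed.
- **Which endpoints are continuous.** Section 12 lists "continuous variables (ICU length of stay, hospital length of stay, duration of mechanical ventilation") and says that they "will be compared between the two arms using Kaplan-Meier curve and log-ran test to take into account data censoring". It does not say when an incomplete stay is censored and when it is missing.

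**The concern.** A sensitivity analysis for missing outcomes should show how far the missing patients would have to differ between arms before the conclusion changes. A rule that moves both arms the same way leaves that out. If loss is about equal, the fills can agree with the complete-case result even though a modest imbalance among the missing patients would remove significance. The result would then be reported as robust without that having been tested.

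This matters most for the primary endpoint. Under Section 20, 28-day status for patients discharged earlier comes from an emailed survey and, failing that, a phone call. Non-response may therefore be related to the outcome. Section 12 promises that all randomized patients will be analysed, yet the reference analysis is complete case, so the sensitivity analysis carries much of that promise.

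The durations raise a separate problem. A partly observed stay carries a known minimum, which censoring preserves. A fixed fill entered as a completed stay discards it.

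**Working it through.** **Inputs (Section 12).** 28-day mortality of 23.3% with 6 mg and 5.9% with the weight-based dose; two-sided 5% test; 80% power; 64 per group; 10% dropout; 71 recruited per arm.

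**Step 1. Reproduce the plan's figure.** With p̄ = (0.233 + 0.059)/2 = 0.146,

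n = [1.96·√(2·0.146·0.854) + 0.842·√(0.233·0.767 + 0.059·0.941)]² / 0.174² ≈ 63.5, rounded up to 64 per group. Power at 64 is 80.3%. The stated sample size reproduces, and this point does not affect it.

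**Step 2. Planned rates with equal loss.** Observed deaths are 0.233 × 64 ≈ 15 and 0.059 × 64 ≈ 4. The missing number is 71 − 64 = 7 per arm. Differences are weight-based minus 6 mg; p-values are chi-squared without continuity correction.

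| Scenario | 6 mg | Weight-based | Difference (points) | p | Fisher p |
|---|---|---|---|---|---|
| Complete case | 15/64 | 4/64 | −17.2 | 0.006 | 0.011 |
| All missing alive (planned) | 15/71 | 4/71 | −15.5 | 0.007 | 0.012 |
| All missing dead (planned) | 22/71 | 11/71 | −15.5 | 0.029 | 0.046 |
| 6 mg missing alive, weight-based dead (not planned) | 15/71 | 11/71 | −5.6 | 0.385 | 0.516 |
| 6 mg missing dead, weight-based alive (not planned) | 22/71 | 4/71 | −25.4 | 0.0001 | 0.0001 |

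The two planned fills agree for an algebraic reason. With a and b observed deaths and m₁ and m₂ missing (6 mg, weight-based), the all-dead difference is (b − a)/71 + (m₂ − m₁)/71. The second term is zero when loss is equal, so both fills give (4 − 15)/71. Only the p-value moves, because the overall death rate rises.

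**Step 3. Tipping point.** Keep the 7 missing 6 mg patients alive (15/71) and add deaths among the 7 missing weight-based patients:

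- 2 deaths: 6/71, p = 0.033.
- 3 deaths: 7/71, p = 0.064.

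Three of seven is enough on the chi-squared test.

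**Step 4. Vary the amount of loss.** With 4 missing per arm (8/142 = 5.6%, just above the trigger), the planned fills give p = 0.004 (16/71 vs 4/71) and p = 0.011 (20/71 vs 8/71). The opposed scenario, 16/71 vs 8/71, gives p = 0.073.

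**Step 5. Unequal loss.**

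- 4 missing on 6 mg and 10 on weight-based: complete case 16/67 vs 4/61, p = 0.007; all dead 20/71 vs 14/71, p = 0.238.
- 0 and 14 missing: all dead 17/71 vs 17/71, p = 1.0, which is the same table as the opposed worst case.

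Here the existing rule does change the conclusion.

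**Step 6. Durations.** Take a patient who withdraws on day 12 while still in hospital. The stay is at least 12 days. If the lower quartile is below 12 and is used as the fill, the recorded stay is impossible.

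Frequency can only be illustrated, because the documents give no stay distribution. Assumptions: lognormal stay, median 8 days, log-SD 0.8, stay ratio 0.7 between arms, day-28 censoring, pooled quartiles entered as events, loss at a uniform time within the stay, 500 replicates. Under these, 36–42% of lost patients had already passed the lower quartile and 7–9% the upper. With 7 lost per arm, the share of trials with p < 0.05 was 63% for complete case, 62% for the lower-quartile fill, 59% for the upper-quartile fill and 31% with opposed quartiles.

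**The case against.** Several stronger readings are tempting, and the documents do not support them.

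- **That the rule cannot test robustness.** A reader might infer this from the equal-loss table. Step 5 shows otherwise. Even with equal loss, the planned fills move the risk ratio from 0.27 (4/71 over 15/71) to 0.50 (11/71 over 22/71).
- **That the quartile rule contradicts the censoring analysis.** It is a conditional sensitivity analysis and does not replace the log-rank comparison. The day-12 patient can be read as already censored under "using Kaplan-Meier curve and log-ran test to take into account data censoring", with the fill kept for durations that are wholly absent. The plan does not say which reading applies, and that is the gap.
- **That the 10% dropout assumption means the rule will be used for durations.** That allowance was made for the primary endpoint. Durations come from the medical record (Sections 11 and 14), and withdrawing patients are asked whether their record can still be followed (Section 16). Participation "will be 28 days or until hospital discharge, whichever occurs first", so a patient lost after discharge may lack 28-day status but has a complete hospital stay.
- **That both arms receive the same quartile.** Quartiles by arm are not excluded.

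It is also fair to say that the opposed scenario with every missing patient at an extreme is one corner of the range. That argues for a tipping-point display over reliance on the corner alone. What stands is that no arm-opposed scenario is planned, and that censored and missing durations are not distinguished.

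**Conclusion.** The concern holds in a limited form. For binary endpoints, 28-day mortality above all, the planned sensitivity analysis is weak when missingness is similar across arms. In the worked case it spans a single difference of −15.5 points, while the missing data allow −25.4 to −5.6, and 3 deaths among 7 missing patients are enough to lose significance. These figures assume the planned event rates, 7 missing per arm and the uncorrected chi-squared test.

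For ICU stay, hospital stay and ventilation duration, the quartile fill does not suit a log-rank analysis and can fall below observed time if applied to a partly observed stay. The 36–42% figure rests on assumed inputs and is an illustration only. This part is a clarification for secondary endpoints. The change should be made before outcome data are seen.

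**What to change.** In the missing-data paragraph of Section 12:

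1. Add an arm-opposed or tipping-point analysis for 28-day mortality and the other binary endpoints. A grid of assumed events among the missing in each arm, marking where the conclusion changes, would serve.
2. State that partly observed durations are censored at last known status under the Kaplan-Meier and log-rank analysis and are never quartile-filled.
3. State that any value imputed for a duration may not be below the time already observed.

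The cost is a few sentences of text and a little more SAS programming, with no new data or patients. The downside is that extreme opposed scenarios may look unfavourable.
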